4.1.2 The mixed model repeated measures (MMRM)

Fitting a MMRM to change from baseline will be used at final analysis. If the dependent variable is assumed to be log-normally distributed, then the value in logarithmical scale will be used for the model.

The reportable results from the model depending on the distribution of the variable will be as stated below.

If the dependent variable is assumed to be normally distributed:

- The LSmeans and their standard errors for each group

- The difference between active groups and placebo (LSmean difference) together with its CI
- The one-sided p-value for the difference between active groups and placebo

If the dependent variable is assumed to be log-normally distributed:

- Back transformed LSmeans for each group, calculated as: EXP (LSmeans of the logarithmic transformation) = Geometric LSMeans and their back transformed Coefficient Variance $\{\text{SQRT} [(\text{EXP} (\text{variance for log transformed data})) - 1]\} * 100 = \{\text{SQRT} [(\text{EXP}(\text{variance for ln(Visit X)} - \text{LN}(\text{Baseline visit}))) - 1]\} * 100$,
- The back transformed difference between active groups and placebo, ratio is calculated as [EXP (LSmeans difference)], together with its back transformed CI, calculated as [EXP(Lower)]; [EXP(Upper)].
- The one-sided p-value of the comparison between active groups and placebo.

Data used in the model come from the scheduled visits as outlined in the footnote of table 3. Fixed effects of the model will be treatment group, visit and treatment*visit interaction. The baseline value and the stratification factors (geographic region and statin therapy intensity at screening) will be used as covariates. Visit within subject will be considered as repeated measurements. Comparisons of MEDI6570 CCI versus placebo, MEDI6570 CCI versus placebo, MEDI6570 CCI versus placebo and pooled MEDI6570 CCI versus placebo will be assessed using the same model. The restricted maximum likelihood (REML) approach will be used for the estimation of the variance and covariance parameters of the linear mixed model; one sided difference test with alpha level at 5% and one-sided 90% CI will be used for the comparisons.

The unstructured covariance structure will be used in the model for the repeated measures. Visit will be expressed as planned days to accomplish the variance-covariance matrix estimation.

In case the model does not converge for any reasons, the compound symmetry (CS) will be used instead of the unstructured (UN). In case the model does not converge with CS or UN, the autoregressive (AR (1)) and Toeplitz will be used.

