4.2 Scientific Rationale for Study Design

4.2.1 Rationale for Study Population

A study population comprising participants with a prior MI and persistent inflammation was chosen because it reflects the population proposed for subsequent clinical development. A majority of participants will also have elevated NT-proBNP.

Patients surviving an MI remain at high risk of mortality and morbidity with the greatest risk occurring within the first 30 days post event (Abu-Assi et al 2016, Jernberg et al 2015, Johansson et al 2017). This increased risk is partially driven by the presence of significant atherosclerosis in the non-infarct related vessels (Momiyama et al 2012, Park 2014, Kato et al 2012), which may become more susceptible to rupture due to the intense inflammatory response, a prerequisite for healing and scar formation triggered by the MI (Frangogiannis et al 2002). This post-infarction inflammatory process peaks within the first and second weeks post-ischemic event and resolves by the third or fourth week (Sun et al 2009). Moreover, evidence from clinical studies suggests that patients with persistent elevation of serum inflammatory biomarkers 4 weeks after an ACS have worse outcomes (de Lemos et al 2007).

NCPV and total plaque volume have been shown to be significant predictors of cardiac events in ACS, with NCPV being a better predictor of a MACE than total plaque volume or calcium score (Kristensen et al 2011). These different components of coronary atherosclerosis during CTA have been shown to be of incremental value for prognostication (Radosavljevic-Radovanovic et al 2016).

In addition, NT-proBNP has been shown to be a strong predictor of future AEs in the post-MI population (Lindahl et al 2005), being more reliable when measured in the relatively stable phase (Kurtul et al 2016). Furthermore, the levels of NT-proBNP were associated with the severity and complexity of the underlying CAD (Kurtul et al 2016).

The lower limit of 30 days post-MI was selected both to refrain from suppressing the necessary inflammatory response and because the expected elevated levels in hs-CRP, cytokines and NT-proBNP during this window may not persist long-term. In addition, this period would allow patients' standard of care medical therapy to be optimized and stabilized before being enrolled in the study. An upper limit of 365 days after the MI was selected to include patients who have a high residual risk of MACE and may derive benefit from

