5 STUDY POPULATION

Prospective approvals of protocol deviations to recruitment and enrollment criteria, also known as protocol waivers or exemptions, are not permitted.

Participants may undergo an optional pre-screening visit upon providing written, informed consent for pre-screening. The optional pre-screening visit is for the purpose of collecting blood samples to assess qualifying biomarker values ([Table 3](#)). The local laboratory may be used for analyzing pre-screening samples. The optional pre-screening visit will not replace the screening visit; all screening visit laboratory samples must be collected and will be used to determine eligibility.

Participants are considered to have enrolled in the study from the time they (or their legally acceptable representatives) sign the first ICF (either the ICF for the optional pre-screening evaluations, or the ICF for the full screening evaluations).

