5.1 Inclusion Criteria

Participants are eligible to be included in the study only if all of the following criteria apply:

- 1 Participant must provide informed consent before any study-specific activities are performed ([Appendix A 3](#)), must be able and willing to meet all requirements for randomization within 42 days after signing the full ICF, and must adhere to the schedules of activities.
- 2 Women must be ≥ 40 years of age at the time of signing the ICF. Men must be ≥ 21 years of age at the time of signing the ICF.
- 3 Participant must:
 - (a) be 30 to 365 days after presumed type-1 (ie, due to plaque rupture or erosion) MI (either STEMI or NSTEMI) at the time of enrollment.
 - (b) have persistent inflammation, defined as hs-CRP ≥ 1 mg/L, as measured centrally at screening Visit 1.
- 4 Participant must have body mass index within the range 18 to 40 kg/m² inclusive.

- 5 For female participants, the participant must not be pregnant or lactating and must be of non-childbearing potential, confirmed at screening Visit 1 by one of the following:
 - (a) Postmenopausal, defined as amenorrhea for \geq 12 months following cessation of all exogenous hormonal treatments, and with luteinizing hormone and follicle stimulating hormone levels in the postmenopausal range.
 - (b) Documentation of irreversible surgical sterilization by hysterectomy, bilateral oophorectomy, or bilateral salpingectomy. Tubal ligation is not considered as irreversible surgical sterilization.
- 6 Participant must have an evaluable, pre-randomization CTA with quantifiable, non-calcified plaque, as confirmed by the core laboratory.

Participants will be reassessed for study eligibility before study intervention is administered on Day 1 (Visit 3). Participants should be considered for a high-intensity statin based on existing guidelines for long-term management of patients after an MI. Participants should ideally be on a stable dose of lipid-lowering therapy throughout the treatment period of the study; therefore, efforts should be made to maximize statin intensity before randomization.

The proportion of participants with an NT-proBNP value < 125 pg/mL at screening who can be randomized to a study intervention may be capped. If this proportion is capped, a baseline NT-proBNP value of ≥ 125 pg/mL will be required for inclusion in the study. During the study, randomization to an intervention group may also be capped within other specific participant subgroups.

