9.4.2.2 Secondary Endpoints

NT-proBNP

Secondary endpoint of relative change from baseline in NT-proBNP will be analyzed based on the ITT population. Relative change from baseline is defined as the ratio of the post-baseline visit value over the baseline value, expressed as a percentage. A MMRM analysis will be performed. The dependent variable is change from baseline for the log-transformed value of NT-proBNP, ie $\log(\text{post-baseline visit value}) - \log(\text{baseline value})$. The results will be back-transformed to the original scale. The model will include fixed effects of treatment group, visit, treatment group-by-visit interaction, and randomization strata, with baseline

NT-proBNP as a covariate. Repeated measures for the model will be visit within subjects. An unstructured covariance structure will be used for the repeated measures. In case the model does not converge, back-up covariance structures and other analysis solutions will be detailed in the SAP.

Secondary Endpoints Derived from Echocardiogram and CTA

Secondary endpoints that are measured by echocardiogram or CTA will be analyzed based on the Echocardiogram or CTA Analysis Population, respectively. ANCOVA analyses similar to the primary endpoint will be performed; the model will adjust for treatment group, respective baseline value, and randomization strata.

Immunogenicity Analyses

The Immunogenicity Population will be used for the immunogenicity analyses.

The number and percentage of participants with confirmed positive serum ADA to MEDI6570 will be reported by dose level. Titer data will be summarized descriptively.

The potential impact of ADA on MEDI6570 PK, efficacy, and safety will be evaluated as data allow.

PK Analyses

The PK Population will be used for the PK analyses.

MEDI6570 serum concentration data will be summarized descriptively, tabulated and plotted.

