4.1.1 Analysis of covariance (ANCOVA)

The ANCOVA model will be used to fit change from baseline at each concerning visit. Data used in the model are data from baseline and the scheduled tested visit. The group of treatment will be considered as a fixed effect of the model while the baseline value and the stratification factors (geographic region and statin therapy intensity at screening) as covariates. Comparisons of MEDI6570 CCI versus placebo, MEDI6570 CCI versus placebo, MEDI6570 CCI versus placebo and pooled MEDI6570 CCI versus placebo will be assessed using the same model. The restricted maximum likelihood (REML) approach will be used for the estimation of the variance and covariance parameters of the linear mixed model; one sided difference test with alpha level at 5% and two-sided 90% CI will be used for the comparisons. No data imputation will be used.

In case of singularity between the covariates (i.e. within each treatment group subjects have exactly the same combination of both stratification factors), the second stratification factor (level of statin therapy) will be removed from the model.

ANCOVA model will be run by subgroup see section [4.2.8.1.5](#), [4.2.8.2.2](#), [4.2.8.3.2](#), [4.2.10.1.1](#) for details. In case of low number of subjects (less than 13 observations) in a subgroup the results will not be provided since there are not estimable or not reliable.

If the parameter is assumed to be normally distributed, the variable fitted in the model will be the change from baseline; the ANCOVA model and the reportable results will be those described below:

- The least-square means (LSmeans) and their standard errors for each group

- The difference between active groups and placebo (LSmean difference) together with its 90% CI
- The one-sided p-value for the difference between active groups and placebo

If the parameter is assumed to be log-normally distributed, the variable fitted in the model will be the change from baseline in logarithmical scale. Change from baseline in logarithmical scale is defined as the log-transformation of the post-baseline visit value minus the log-transformation of the baseline value.

The ANCOVA model will be as described above but the reportable results from the model will be:

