4.2.8.1.5 Subgroup Analysis of CTA endpoints

Subgroups planned for analysis include but are not limited to those defined by randomization (by IVRS) stratification factors. Stratification factors include geographic region (Asia, North America, Rest of the World) and statin therapy status (no, low or moderate and high intensity statin therapy).

A complete list of the subgroups ((*subgroup level 1*; *subgroup level 2*; ...; *subgroup level x*) analysed at the final analysis for NCPV_{MD} and NCPV is provided below.

- Sex (*Male; Female*)
- Age (<65 ; ≥ 65 years)
- Race (*Caucasian; Non-Caucasian*)
 - with *Caucasian* = White and *Non-Caucasian* = American Indian or Alaska Native, Asian, Black or African American, Native Hawaiian or Other Pacific Islander, Other.
- Geographic region
 - *Asia, North America; Rest of the World*
 - *Western (North America and Rest of the World); Asia*
Asia will not be repeated in the second subgroup.
- Diabetes mellitus (*Presence; Absence*)
 - with *Presence* = if diabetes mellitus (type 1 or type 2) in Medical History (MH) or Cardiac History and Risk Factor (SPECHIS) forms and *Absence* otherwise.
- Smoking Status (*Smoker; Non-smoker*)
 - with *Smoker* = current or former smoker and *Non-smoker* = never smoked.
- Qualifying MI Type (*STEMI; NSTEMI*)
 - using Indication field from Coronary Revascularisation - Qualifying Event (PROCCA) form
- Baseline eGFR (<60 mL/min/1.73 m²; ≥ 60 mL/min/1.73 m²)
- Statins (*None/Low/Moderate intensity; High intensity*)
- Baseline NT-ProBNP
 - ($<$ Median; \geq Median)
 - ($<$ 125 pg/mL; \geq 125 pg/mL)
- **CCI**
[REDACTED]
- Baseline Global NCPV ($<$ Median; \geq Median) to be performed only for Global NCPV using baseline value computed after segment matching to Day 253
- Baseline NCPV_{MD} ($<$ Median; \geq Median) to be performed only for NCPV_{MD}

using baseline value computed after segment matching to Day 253

- Baseline LDL ($<70 \text{ mg/dL}$; $\geq 70 \text{ mg/dL}$)
- Coronary intervention/revascularisation (for qualifying event) (Yes, No)
using Type of coronary procedure from Coronary Revascularisation - Qualifying Event (PROCRA) form
- Time from the date of qualifying event to randomization ($<3 \text{ months}$; $\geq 3 \text{ months}$)
in case of multiple qualifying events, the latest event is used.
- Baseline LVEF ($<50\%$; $\geq 50\%$)

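### The NT-proBNP and echocardiographic models leave out time since MI, a baseline variable the SAP already derives, at a modest cost in precision

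*SAP*

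**What the plan says.** Inclusion criterion 3(a) in Protocol 5.1 requires participants to "be 30 to 365 days after presumed type-1 (ie, due to plaque rupture or erosion) MI (either STEMI or NSTEMI) at the time of enrollment". Protocol section 5 fixes when that clock is read: "Participants are considered to have enrolled in the study from the time they (or their legally acceptable representatives) sign the first ICF". Pre-screening and screening may each take up to 42 days after that.

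Protocol 4.2.1 explains the 30-day lower limit partly by saying that the "expected elevated levels in hs-CRP, cytokines and NT-proBNP during this window may not persist long-term". It also describes NT-proBNP as more reliable once the patient is relatively stable.

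The models do not use time since MI:

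- **NT-proBNP.** Protocol 9.4.2.2 gives "fixed effects of treatment group, visit, treatment group-by-visit interaction, and randomization strata", with baseline NT-proBNP as covariate. SAP 4.1.2 agrees: "The baseline value and the stratification factors (geographic region and statin therapy intensity at screening) will be used as covariates".
- **LVEF and GLS.** The ANCOVA in SAP 4.1.1 takes "the baseline value and the stratification factors (geographic region and statin therapy intensity at screening) as covariates".
- **Randomization.** Protocol 6.3.1 stratifies by region and statin intensity only.

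The variable nevertheless exists in the plan. The CTA subgroup list in SAP 4.2.8.1.5 includes "Time from the date of qualifying event to randomization", split at 3 months, with a rule that the latest event counts if there are several.

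**The concern.** Two participants with the same baseline NT-proBNP, one dosed soon after day 30 and the other about a year after MI, may have different expected untreated change to Day 253. The protocol's own rationale for the lower limit gives a reason to expect this. Baseline adjustment removes only part of such a difference, because the same value can be a falling level in one participant and a settled level in the other. Whatever remains stays in the residual error of the treatment comparison.

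At stake is precision on secondary endpoints for which the readable documents state no power, in a trial whose planned size Amendment 2 cut from 792 to 400.

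**Working it through.** **What the plan's own figures allow.** The Synopsis plans 111 evaluable participants in each of two dose groups and in pooled placebo, plus 27 in the legacy group: 3 × 111 + 27 = 360, as stated. The SD and power behind the 11 mm³ primary target are redacted, so 111 itself cannot be reproduced.

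**Spread of time since MI at randomization.** The lower end is about 30 days. The upper end is 365 + 42 + 42 = 449 days, because the limit applies at first consent.

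**Value of adjustment.** Let R² be the share of residual variance, after baseline adjustment, that time since MI explains. The documents give no value, so R² is assumed at 1%, 4% and 9%. The SE is multiplied by √(1 − R²), and the equivalent sample size is 111/(1 − R²). For an endpoint with 80% power at one-sided 0.05, the new power is Φ[(1.645 + 0.842)/√(1 − R²) − 1.645].

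| Assumed R² | SE reduction | Equivalent n per arm | Gain over 111 | Power from 80% |
|---|---|---|---|---|
| 1% | 0.5% | 112.1 | 1.1 | 80.3% |
| 4% | 2.0% | 115.6 | 4.6 | 81.4% |
| 9% | 4.6% | 122.0 | 11.0 | 83.2% |

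**NT-proBNP example.** Take a 25% reduction, which Protocol 4.2.2.2 mentions as a benchmark but which is no longer a powering target. The difference is −ln 0.75 = 0.288 log units, with 111 per arm and an assumed SD of log change.

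- SD 0.8: SE = 0.8 × √(2/111) = 0.107 and power is 84.9%. It becomes 85.3%, 86.2% and 87.8% at R² of 1%, 4% and 9%.
- SD 1.0: power is 69.1%. It becomes 69.5%, 70.6% and 72.6%.

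**Is 1% to 9% plausible?** An illustrative simulation assumed uniform entry from day 30 to 365, an NT-proBNP excess at day 30 of 0.3 to 1.0 log units decaying with a time constant of 60 to 120 days, and residual SD 0.6 to 0.8. Log time since MI then explained about 0.7% to 13% of the variance left after baseline adjustment. With an excess of 0.5 to 0.7 log units the range was about 2% to 7%. Only the largest excess with the smaller SD went above 9%. Every one of these inputs is assumed.

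**Chance imbalance.** With n per arm, the between-arm difference in standardized mean time since MI has SE √(2/n), which is 0.134 at n = 111. A one-SE imbalance moves the estimate by √R² × 0.134 outcome SD: 0.027 at R² = 4% and 0.040 at 9%. The treatment SE is also 0.134 outcome SD, so the shift is √R² of it, or 0.2 and 0.3. At an assumed 28 per arm both quantities grow to √(2/28) = 0.267, and the ratio stays at 0.2 and 0.3.

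**The case against.** The strongest reply is that this is a choice, not an error. The SAP covariates match the protocol, allocation is randomized, and the SE and confidence interval already allow for chance imbalance. That stands. A reader might infer biased treatment effects or an inflated type I error, and neither follows.

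It can also be said that the sentence in Protocol 4.2.1 most naturally refers to the first 30 days, which the design excludes, and that the same section says the inflammatory process resolves by the third or fourth week. That weakens the point without removing it. The resolution statement concerns inflammation, and nothing in the section says NT-proBNP has settled by day 30.

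Three further readings are tempting and not supported:

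- **That the protocol documents spontaneous LVEF recovery.** Section 4.2.2.2 says only that LVEF change after MI predicts outcome and that treatment can improve LVEF. It gives no time course for LVEF or GLS, so the case for the echo endpoints is weaker than for NT-proBNP.
- **That the NT-proBNP and echo subgroup lists certainly omit time since MI.** SAP 4.2.8.2.2 and 4.2.8.3.2 contain redacted bullets. The item is printed in clear in the CTA list, so it is probably not what is hidden, but absence is unproven. A subgroup split would not reduce noise in any case.
- **That the LVEF below 50% analyses face a special risk.** Imbalance is larger in small arms, but the SE grows with it, as shown above.

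**Conclusion.** The point holds as a precision improvement. The readable NT-proBNP and echo models omit a baseline variable that the trial already derives and that the protocol gives some reason to think prognostic, at least for NT-proBNP. Under the assumed 1% to 9% of residual variance, the loss is about 1 to 11 participants per 111 per arm, or roughly 0 to 3 power points (3.5 in the least favourable NT-proBNP example). That size rests wholly on assumption, since the documents supply no natural-history slope and no SD for these endpoints. The validity of the planned tests is not in question.

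**What to change.** - **SAP 4.1.2:** add log(days from qualifying MI to randomization) and its interaction with visit to the NT-proBNP model. The interaction matters because the model uses both Day 113 and Day 253, and any time-since-MI effect on change may differ between them.
- **SAP 4.1.1:** add the same covariate for LVEF and GLS, including the analyses restricted to baseline LVEF below 50%. Keep the existing rule that the latest qualifying event is used.
- **SAP section 6:** record the addition, because Protocol 9.4.2.2 lists the model terms without it.

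The cost is one degree of freedom in the ANCOVA, two in the repeated-measures model, and a few lines of text. Protocol 9.4 allows SAP amendments before unblinding, and the variable needs no new data.

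Two further steps are optional. The covariate could be extended to the CTA endpoints, though no passage shows that plaque change depends on time since MI. The 3-month split could be added to 4.2.8.2.2 and 4.2.8.3.2 for description, but it would not improve precision and would add further unadjusted comparisons.

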4.1.3 Cox Proportional Hazards model

Time to event analyses will be performed using Cox Proportional Hazards model. The reportable results from the model will be as stated below:

- Number and percentage of subjects with event
- Hazard ratio for active groups versus placebo and its 90% CI

- The one-sided p-value for the comparison between active groups and placebo

The hazard ratio with corresponding CI and p-value for treatment comparisons will be presented, fitted by a Cox Proportional Hazards model including stratification factors (geographic region and statin therapy intensity at screening). The Kaplan Meier Estimate at Day 326 will also be provided for each group. Comparisons of MEDI6570 [REDACTED] CCI versus placebo, MEDI6570 [REDACTED] CCI versus placebo, MEDI6570 [REDACTED] CCI versus placebo and pooled MEDI6570 [REDACTED] CCI versus placebo will be assessed using the same model.

